FINAL PROTOCOL AND STATISTICAL ANALYSIS PLAN

Spine Pain INtervention to Enhance Care quality And Reduce Expenditure (SPINE CARE) – Randomized Clinical Trial

NCT03083886

10-01-2021

FINAL PROTOCOL

1. Synopsis

Low back and neck pain are among the leading causes of medical visits, lost productivity and disability. There is an urgent need to identify effective and efficient ways of helping subjects with acute spine pain while guiding practitioners towards high-value care. This trial will be a block and cluster-randomized open-label multi-centered pragmatic randomized clinical trial comparing healthcare spending and clinical outcomes for subjects with spine pain of less than three months' duration, in whom there are no red flag signs or symptoms. Subjects will be randomized to one of three treatment strategies: (1) usual primary care provider-led care; (2) usual PCP-led care with spine pain treatment directed by the Identify, Coordinate, and Enhance decision making (ICE) care model, and (3) usual PCP-led care with spine pain treatment directed by the Individualized Postural Therapy (IPT) care model. Our outcomes of interest will be spine-related healthcare utilization at one year as well as pain and functionality of the study participants.

2. Background

Direct healthcare spending on neck and back pain (spine pain) exceeds \$86 billion annually in the United States. While up to 80% of adults will experience clinically significant spine pain during their lifetimes, only a minority will progress to chronic pain with resultant high health care utilization (1–9). For the vast majority of subjects, spine pain complaints are self-limited (10–12). As a result, there is little evidence that the large amounts currently spent on spine pain has significantly improved population outcomes.

Many clinical guidelines exist for the treatment of spine pain, but much of the evidence supporting specific treatment modalities addresses subjects with chronic back pain rather than individuals presenting with more acute or subacute complaints (13). Despite many clinical guidelines for the management of low back pain, research in this area has shown mixed results and has led to a non-uniform clinical approach to treating spine pain with predictably variable outcomes of pain progression (14–16). Many patients with low back pain begin to incur substantial resource use and associated expenses soon after their first episode of pain (14). For example, there is mounting clinical evidence that imaging offers little help for the initial care of a subject with nonspecific spine pain (17,18), but despite the lack of utility therein, nearly 15% of clinicians admit it would be difficult to not order advanced imaging when subjects present for care (15).

Currently there is also widespread use of non-traditional modalities of care, such as comprehensive and alternative medicine (CAM). A recent study suggested that 30% of subjects are using CAM, and 42% of those subjects did not disclose this to their primary care physician (19). A particularly promising strategy appears to be exercise or postural therapy, which is defined as “a series of specific movements with the aim of training or developing the body by a routine practice to promote good physical health (20–23).” Despite this, there are substantial inconsistencies in the literature and many of the existing studies have been of low-quality (20). Given the discordance between number of subjects using these techniques and the amount of reliable data by which to judge their effectiveness, it is necessary to perform a rigorous evaluation.

One strategy for enhancing the efficiency of spine pain interventions is to target them at individuals with a high probability of progressing from acute to chronic pain. For example, the STarT Back tool uses a biopsychosocial framework to identify features of a subject that helps to predict the likelihood of developing chronic pain, which can then direct treatments to improve pain and functioning (24). Applying this risk stratification method to subjects with low back pain (24,25) and guiding treatment based upon it has been shown to improve clinical outcomes and reduce health spending (26). However, the majority of subjects included in the studies evaluating the STarT Back tool had been experiencing back pain for more than three months and thus, further research is needed to risk stratify subjects earlier in the course of their illness to prevent the transition of acute pain into chronic pain. These strategies must also be well-received by providers, as acceptance of these new treatment pathways has been limited (27).

The SPINE CARE trial seeks to fill the gaps in our knowledge about how to manage subjects presenting with acute and subacute spine pain by rigorously evaluating two methods of care: Individualized Postural Therapy (IPT) and the Identify, Coordinate, and Enhance decision making (ICE) Care Model developed by the Clinical Excellence Research Center (CERC) at Stanford University. These two models of care represent novel approaches to the comprehensive treatment of subjects with spine pain with the potential to significantly reduce spine related cost of care and improve clinical outcomes.

3. Objectives and Overall Design

This block and cluster-randomized, open-label, multi-centered three-arm pragmatic randomized clinical trial seeks to compare healthcare spending, pain, physical functioning, and

quality of life for subjects with acute and subacute spine pain receiving care in one of three ways: (1) usual primary care provider (PCP)-led care; (2) usual PCP-led care with spine pain treatment directed by the ICE care model, and (3) usual PCP-led care with spine pain treatment directed by the IPT care model. ICE and IPT will both be integrated with typical clinical practice to test strategies that, if effective, could easily be incorporated into existing models of care. We hypothesize that the ICE and IPT models of care will decrease spine related healthcare spending while improving physical functional and quality of life.

4. Study Setting

This trial will be conducted in primary care clinics in geographically distinct areas in the U.S. with the following characteristics:

1. Provide primary care to adult subjects with acute back and neck pain.
2. Offer same day or next day appointments.
3. Do not have an existing specialized program for back or neck pain subjects.
4. Are located within 30 minutes driving distance of an Individualized Postural Therapy clinic.
5. Agree to equipoise for all study arms and study protocol, and defer spine related pain treatment direction to ICE staff for subjects randomized to the ICE treatment arm.

The sites will be selected so as to not have overlapping clinical staffs in order to minimize the risk of contamination (given that sites are cluster randomized) and to thereby minimize the possibility that subjects at control sites will be exposed to potentially beneficial aspects of either of the interventions.

5. Subjects

5.1. Inclusion Criteria

- Patients with back or neck pain of ≤ 3 months' duration. All patients must have spine pain with or without radiation to the extremities or the head
- Age ≥ 18 years
- Willing and able to provide informed consent

5.2. Exclusion Criteria

- Patients with symptoms attributed to the spine but without actual pain in the spine (e.g. those with cervicogenic headache without neck pain)
- Currently pregnant
- Currently receiving disability benefits, worker's compensation, or involved in litigation for a workplace injury
- Currently enrolled in another intervention trial for the management of acute back or neck pain
- Cancer that is metastatic or being actively treated. (i.e., chemotherapy, radiation, surgery)
- History of receiving active therapy for back or neck pain in the past 3 months (7+ consecutive days of narcotic use, 6+ sessions of PT, chiropractic care, acupuncture, postural therapy, or other spine therapy delivered by a trained provider)
- History of spine surgery or spine injections/ablation in the past 6 months
- Severe, active psychosis or major depression inhibiting ability to physically participate in intervention
- Red Flag Symptoms (fever, night sweats, unintentional weight loss, bowel or bladder dysfunction, neurologic weakness, current intravenous drug use)

6. Interventions

Clinics will be randomized to one of the following three arms as described below.

6.1 ARM 1: Usual care

Subjects seeking care at a clinic assigned to this arm will receive usual care as directed by their primary care provider. Treatment modalities may include medications, specialty referrals, imaging, procedures such as injections, physical and psychological therapy, as appropriate.

[figure not shown]
6.2 ARM 2: PCP-led care + ICE

Subjects seeking care at a clinic assigned to this arm will receive the ICE care model through referral by their primary care provider. The ICE care model was developed by the Clinical Excellence Research Center at Stanford University based on a review of the peer-reviewed literature for adult subjects with incident neck or back pain who are not using high-dose opioid medications or receiving spine-related long-term disability payments. The care pathway is designed to take place over the course of six weeks and is intended to avoid low-value healthcare expenditures for subjects presenting with spine pain by:

1. Stratifying subjects with back or neck pain into “low” and “high” risk groups, based on the STarT Back risk assessment tool (Appendix A) (25), and directing care accordingly (Figure 1). The STarT Back tool is a validated instrument that was created to assist with the prediction of the transition of acute to chronic pain. This tool measures a subject’s physical functionality as well as their experience with pain by determining how much

their pain causes psychological distress that may magnify the disability caused by the pain itself. Baseline STarT Back tool responses have been shown to be predictive of pain intensity at six months (28).

Figure 1. Care Stratification Based on STarT Back Scoring Tool (©Keele University 01/08/07 Funded by Arthritis Research UK)

2. Directing low-risk subjects with uncomplicated back or neck pain and few psychosocial risk factors to a limited physical therapy course without additional diagnostic evaluation or specialty referral (Table 1). If subjects do not improve, they will be referred back to their primary care providers for further evaluation and treatment.
3. Referring high- and medium-risk subjects with significant biopsychosocial risk factors (i.e., a high degree of pain catastrophizing) predictive of chronicity to a novel spine team which focuses treatment on physical rehabilitation, normalization of experience, and self-management skills. The team will consist of a physical therapist serving as the

rehabilitation lead, a “Spine Coach” focusing on enabling subject self-motivation and an “ICE MD” who fulfills an advanced medical consultation role for those who do not improve after initial course of therapy. The Spine Coach is a psychology counselor trained in motivational interviewing and supportive care delivered by telephone.

The specific components of the ICE model are summarized below:

Table 1. Levels of care: Proposed frequency of contact

Subject Risk	Physical Therapy	Spine Coach	ICE MD
Low risk	1 session*	1 session	None. Patients who do not improve in six weeks will return to usual care.
High and medium risk	Up to 3 sessions	Up to 3 sessions†	Consult to provide an individual treatment plan for all subjects.

*If subject has improved prior to visit they will be able to cancel PT session in the conservative care pathway.

†Frequency will be determined by subject and spine coach

Responsibilities of the ICE care providers will be as follows:

1. **Physical Therapy (PT)** – The ICE PT will perform their typical practice of taking a detailed history pertinent about the subject’s spine pain, perform a thorough physical exam, and then tailor the frequency and goals of therapy based on the subject’s STarT Back risk level. Each practitioner will be trained to communicate with subjects using enabling language that reinforces self-efficacy skills and provides tools for self-management. These encounters will take place in a local physical therapy practice commonly used by participating referring clinics that are willing to undergo training about the ICE pathway.
2. **Spine Coach** – The Spine Coach will use motivational interviewing to teach coping skills, improve subject self-efficacy, and provide ongoing reinforcement. These encounters will

occur by telephone with frequency directed by the STarT Back tool. Subjects who are at low risk for chronicity will receive one call whereas individuals who are medium or high risk will receive up to three calls over the first six weeks of the intervention. The coach will provide recommendations on self-management, guided by principles in the Back Book (29) and normalize the subject's experience. The Back Book was developed to explain the most common causes of musculoskeletal spine pain, and ways to stay active while recovering. The first outreach will take place within 3 business days of the initial visit to the PCP for spine pain to the primary care provider and be provided at regular intervals based on the needs of the subject, as agreed upon by the spine coach and subject. The Spine Coach and the Physical Therapist will coordinate care using a Communication Checklist (Appendix K) after each visit.

3. **ICE MD** – All subjects who are stratified to high or medium risk by the STarT Back Tool as well as low-risk subjects who have no improvement in their pain despite treatment with the ICE pathway for 6 weeks will receive an ICE MD consultation. The ICE MD will be an MD or DO with pain medicine or physical medicine and rehabilitation specialty experience. They will be experienced in conservative musculoskeletal care and have an active medical license in the state in which they are providing consultations. All assessments by the ICE MD will occur remotely via chart review of the subject's electronic health record available through their primary care provider's office in conjunction with any study communication between the physical therapy team and spine coach. Based on review of this information, individualized treatment

recommendations will be provided to the primary care provider in a written summary that can then be carried out at the discretion of the primary care provider (Appendix B).

6.3. ARM 3: PCP-led care + IPT

The Individualized Postural Therapy (IPT) is an alternative method of care for subjects with neck and back pain. This intervention was chosen to be representative of an alternative care model that is commonly used by individuals with back pain, either in conjunction with, or as an alternative to, usual care.

IPT involves the evaluation of a subject's posture to identify postural and alignment deviations and, based on this, a personalized corrective exercise program is prescribed. This method does not involve the use of prescription medications, surgery, or manipulation. The initial consultation typically takes between 60-90 minutes, at which time a regimen of exercises is provided. The exercise menu consists of exercises, specific to the individual, which take between 15-75 minutes daily and can be performed at home once the subject has been evaluated by an IPT clinician. The amount of exercise required depends on the individual's postural and mechanical dysfunctions, and time allowance. A treatment course typically lasts eight sessions over eight weeks. In order to allow for the consistent delivery of this arm of the study at multiple study-sites across the country, IPT will be delivered by The Egoscue Method (30). Egoscue was founded in 1971 and has 25 clinics worldwide.

7. Study Procedures

7.1 Randomization

Randomization will occur at the clinic level (i.e. subjects will be cluster randomized) in a 1:1:1 ratio to usual care, usual primary care + ICE, and usual primary care + IPT. To ensure adequate balance between the treatment arms with respect to sample size practices will be categorized into blocks of 3 based on the average number of patients with spine pain that they see in a typical week, their location, and/or their provision of other services such as urgent/walk-in care. Because of differences between the delivery networks participating in the trial, the stratification factors may differ by location. Randomization will occur within these blocks.

7.2 Subject Identification

The study will include individuals presenting for care with a chief complaint of back pain or neck pain. Potentially eligible subjects will be identified by reviewing clinic schedules for upcoming visits and/or through screening when they present to the clinic for “same-day” or “walk-in” care.

7.3 Eligibility Screening

Patients presenting for care with spine pain will be informed of the study when they arrive for care and will be given a screening form to assess them for eligibility. Subjects who meet the initial eligibility criteria will be given either a written informed consent form (Vanderbilt and UBC, Appendix D) or a verbal informed consent form (HonorHealth, Appendix

D) detailing the potential benefits and risks of participating in the study, and what would be required of them. Consenting subjects will then be asked to complete the baseline surveys while waiting to be seen by their primary care provider. Their primary care provider will confirm that their symptom criteria are completed correctly and evaluate them for additional exclusion criteria that require clinical expertise (Appendix E). Subjects who meet all the inclusion and exclusion criteria will be enrolled in the study.

7.4 Baseline Surveys

After providing consent, subjects will be asked to complete the baseline demographic data (Appendix F) and other baseline surveys (Table-3) using the study's electronic data capture system (see Section 9.3).

7.5 Subject cost-sharing

Subjects randomized to the usual care arm will pay standard copayments as determined by their insurance carrier for all services recommended by their PCPs. Subjects randomized to the ICE or IPT will face no out-of-pocket costs for study recommended visits but will, as in the usual care arm, pay standard copayments as determined by their insurance carrier for other services recommended by their PCPs.

8. Informed Consent

Vanderbilt and UBC sites will be required to obtain subject authorization to participate in the study using written informed consent at the time of their enrollment clinic visit.

HonorHealth sites will be required to obtain verbal consent for the subject to participate in the study. Information about the trial and the requirements of trial participation will be summarized in an informed consent document, whether verbal or written consent is obtained (Appendix D).

9. Outcomes

9.1 Primary Outcomes

The two primary outcomes for the trial will be: (a) spine-related cost of care at one year and (b) change in pain at three months as assessed by the Oswestry Disability Index (ODI, Appendix G). Secondary outcomes will include pain at 12 months, quality of life at 12 months assessed using the EQ-5D, and self-efficacy at 12 months assessed using a scale developed by Lorig et al. (31).

Table 2: Outcomes

Primary	Spine related cost of care at one year Change in pain (measured by ODI) at three months
Secondary	Change in pain (measured by ODI) at one year Quality of life (measured by EQ-5D) at one year Self-efficacy (measured by scale developed by Lorig et. al) at one year

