10.1 Analysis plan

All analyses will be performed using intention to treat principles based on study arm with which a subject is assigned at study enrollment and regardless of whether or not all protocol steps have been completed. We will report means and frequencies of pre-randomization variables separately by study arm. Comparison of these values will be made with generalized estimating equations to adjust for the block and cluster randomized design.

Because cost data in healthcare is not normally distributed (32) due to significant zero data representing subjects for whom there is little to no cost, we will have to model the data accordingly. We will evaluate the two primary outcomes, total cost of care, using generalized estimating equations with gamma distributed errors and an identity link function which can account for a positively skewed distribution. Changes in ODI from baseline to three months will be compared for the treatment arms using generalized estimating with normally distributed errors and an identity link function. All models will adjust for age and sex, account for the cluster and block randomized study design and include fixed effects for the 3 different delivery networks that were used for recruitment. In secondary analyses, we will repeat our models adjusting for unmatched confounders that remained despite randomization. Our primary analyses will compare each of the two treatment arms separately with usual care (i.e., ICE compared with usual care and IPT with usual care). Because we are evaluating two primary

outcomes, we will use a Bonferroni-corrected two-tailed type 1 error of 0.025. Analysis of secondary outcomes will also be performed using generalized estimating equations with error distributions and link functions appropriate to the outcomes being evaluated.

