Missing data will be accounted for using multiple imputation (51), which has been determined an adequate strategy to minimize both false positive and false negatives in clinical trials. We will perform 20 imputations using Proc MI in SAS with a fully conditional specification. The following variables will be used to perform the imputation: age, study arm, study site, clinic, sex, race/ethnicity, BMI, exercise frequency at baseline, education level, employment status, smoking status, other medical conditions at baseline, number of medications used for spine pain at baseline, length of pain at baseline, number of previous pain episodes, STarT back score, baseline ODI, baseline self-efficacy, baseline EQ-5D, and scores for patient-reported outcomes at every follow-up timepoints (ODI, cost, Lorig self-efficacy scale, and EQ-5D).

As resource utilization and ODI were collected at multiple time points, we will also evaluate non-missing cost and ODI data from each time point using a repeated measures design. In specific, we will use generalized estimating equations, with link functions and error distributions appropriate to the study outcomes, to assess changes in outcomes over the 12 months of follow-up, while accounting for correlations in the repeated measurements. For spine-related health spending, these analyses will be conducted using the time intervals at which raw data were collected as well as after converting estimates to evenly-spaced months. Because cost data in healthcare is not normally distributed with zero values for participants with no resource utilization during follow-up, we will winsorize estimated costs at the 95th

percentile in secondary analyses. We will report relative spending differences with confidence intervals and a two-tailed p value. As a sensitivity analysis, we will conduct a complete-case analysis on all non-missing values.

Exploratory analyses will be performed evaluating the effect of the interventions on cost in various strata of clinical interest, including age, sex, STarT Back risk group, location of pain, and whether or not this was the subject's first pain episode. We will also evaluate the percentage of subjects in each arm with a decrease in ODI of six points at three, six, and twelve months of follow-up.

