Because cost data in healthcare is not normally distributed (32) due to significant zero data representing subjects for whom there is little to no cost, we will have to model the data accordingly. We will evaluate the two primary outcomes, total cost of care, using generalized estimating equations with Poisson distributed errors and a log link function which can account for a positively skewed distribution. Changes in ODI from baseline to three months will be compared for the treatment arms using generalized estimating with normally distributed errors and an identity link function. All models will adjust for age and sex, account for the cluster and block randomized study design and include fixed effects for the 3 different delivery networks that were used for recruitment. In secondary analyses, we will repeat our models adjusting for unmatched confounders that remained despite randomization. Our primary analyses will compare each of the two treatment arms separately with usual care (i.e., ICE compared with usual care and IPT with usual care). Because we are evaluating two primary outcomes, we will use a Bonferroni-corrected two-tailed type 1 error of 0.025. Analysis of secondary outcomes will also be performed using generalized estimating equations with error distributions and link functions appropriate to the outcomes being evaluated.

Missing data will be accounted for using multiple imputation (51), which has been determined an adequate strategy to minimize both false positive and false negatives in clinical trials. We will perform 20 imputations using Proc MI in SAS with a fully conditional specification. The following variables will be used to perform the imputation: age, study arm, study site, clinic, sex, race/ethnicity, BMI, exercise frequency at baseline, education level, employment status, smoking status, other medical conditions at baseline, number of medications used for spine pain at baseline, length of pain at baseline, number of previous pain episodes, STarT back score, baseline ODI, baseline self-efficacy, baseline EQ-5D, and scores for patient-reported outcomes at every follow-up timepoints (ODI, cost, Lorig self-efficacy scale, and EQ-5D).

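### The 12-month ODI secondary outcome is a level in the text and a change in the table, and no baseline term in the main models makes the two readings equivalent.

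*Combined protocol and SAP*

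**What the plan says.** Protocol section 9.1 lists the secondary outcomes in prose as "Secondary outcomes will include pain at 12 months, quality of life at 12 months assessed using the EQ-5D". Table 2, directly below, gives the ODI entry as "Change in pain (measured by ODI) at one year". The SAP repeats the same prose and the same entry in its section 1 and its Table 1. In both documents the preceding sentence calls the three-month primary outcome a change.

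The analysis plan (protocol 10.1; SAP Statistical considerations, section 1) fixes the response form for the primary ODI outcome only: "Changes in ODI from baseline to three months will be compared for the treatment arms". For the secondary outcomes it says: "Analysis of secondary outcomes will also be performed using generalized estimating equations with error distributions and link functions appropriate to the outcomes". On covariates it says: "All models will adjust for age and sex, account for the cluster and block randomized study design and include fixed effects" for the three delivery networks. Baseline ODI is not among them. It does appear in the list of imputation variables: "STarT back score, baseline ODI, baseline self-efficacy, baseline EQ-5D". A further statement allows later adjustment without naming variables: "In secondary analyses, we will repeat our models adjusting for unmatched confounders that remained despite randomization".

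**The concern.** An analyst working from the prose would model the 12-month score. One working from the table would model the score minus its baseline. With no baseline term the two give different estimates and p-values in any realised sample, and nothing in the analysis section says which is meant. The choice could therefore be made after seeing which arm started worse.

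This design gives some reason not to assume the arms start level. Clinics are randomized (section 7.1). Subjects consent and complete baseline surveys afterwards, at clinics already assigned (7.3). The trial is open-label (section 3). Study visits are free to subjects in the ICE and IPT arms, while usual-care subjects pay copayments (7.5). Who agrees to enrol could differ by arm.

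**Working it through.** **Inputs from the documents (10.2).** 1,032 per arm, 33 clusters (taken as 11 per arm under 1:1:1 allocation), 10% loss, ICC 0.01 (stated in sizing the cost outcome), and a 6-point ODI difference.

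**Assumed, because the documents do not give them.** ODI SD 15 to 18; correlation ρ between baseline and 12-month ODI of 0.2 to 0.7; two-sided alpha 0.05 for secondary outcomes.

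**1. The plan's own figures.**
- Retained per arm: 1,032 × 0.9 = 928.8, or 928.8 / 11 = 84.4 per clinic.
- Design effect: 1 + (84.4 − 1) × 0.01 = 1.834.
- Effective size: 928.8 / 1.834 = 506 per arm.
- Cost calculation, with SD 1.25 times the mean in each arm (1.25 and 1.00 on the usual-care scale): n = (1.25² + 1.00²) × (1.960 + 0.842)² / 0.20² = 502.8. Then 502.8 × 1.834 / 0.9 = 1,025, against the stated 1,032, so the sizing is reproduced to within 0.7%.
- The stated power above 98% for 6 ODI points comes without an SD and cannot be reproduced exactly. With 506 effective subjects per arm it holds for any SD up to about 23.8 at alpha 0.05.

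**2. Gap between the two estimates.** Level estimate minus change estimate equals the between-arm difference in baseline ODI. In the planned models this is the difference after adjustment for age, sex and network, so it is close to the raw difference but not identical. From chance alone, at SD 15:
- SD of the gap = 15 × √(2 / 506) = 0.94 points (1.13 at SD 18).
- Mean absolute gap = 0.94 × √(2/π) = 0.75 points.

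**3. Precision.** SE(level) = 0.94. SE(change) = 0.94 × √(2(1 − ρ)), which is 1.12 at ρ = 0.3, 0.94 at 0.5 and 0.73 at 0.7. The two estimates have correlation √((1 − ρ)/2). With no systematic imbalance they have the same expected value, so only the noise differs.

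**4. How often the two versions disagree on significance** (normal approximation, SD 15-18, ρ 0.2-0.7, no systematic imbalance):

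| True effect (points) | Disagreement |
|---|---|
| 0 | 7-9% |
| 1 | 14-28% |
| 2 | 28-40% |
| 3 | 11-30% |
| 4 | 1-18% |
| 6 | 0-1.3% |

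**5. Cross-check by simulation.** This used a t-test on clinic means, SD 15, ICC 0.01, 11 clinics per arm, 84 per clinic, ρ 0.3-0.7 and a between-clinic correlation of 0.7. Disagreement was about 27-30% at 2.5 points, 2-3% at 4 and about 0% at 6. The normal approximation at 2.5 points and SD 15 gives 24-29% over the same ρ. At an assumed ICC of 0.03 the mean gap rises to 1.0 point, and disagreement is 37-41% at 2.5 points, 17-19% at 4 and about 1% at 6.

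Power at 2.5 points (ICC 0.01) was 71% for level, 70-90% for unadjusted change and about 80-94% with baseline as a covariate.

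**6. Systematic imbalance.** If enrolment produced a 2-point baseline difference (an assumption; SD 15), the two estimates would differ by 2 points on average. Disagreement would be roughly 28-38% with no effect and 55-84% at a 2-point effect, but still below 1% at 6 points.

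**The case against.** The documents lean towards change. Both outcome tables say so, the three-month ODI is a change, and the exploratory responder analysis counts a fall of six points, including at 12 months. The prose list is terse and may simply be shorthand for the table below it. No section plans a level analysis of 12-month ODI. This stands, and it makes change the natural wording to adopt. It does not close the gap, because the response form for this outcome is never stated where the models are defined.

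The secondary analysis that adjusts for residual imbalance could take in baseline ODI. It names no covariates, so it leaves the question open.

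A reader might infer that the two versions would often disagree on significance. The documents do not support that. The only ODI effect they give is 6 points, where disagreement is at most 1.3% under the main assumptions. The 2.5-point effect is an assumption, and it lies near the peak of disagreement.

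A reader might also infer that this outcome is the only check on whether a three-month benefit lasts. It is not: the plan also has a repeated-measures ODI analysis over 12 months and the responder percentage at 12 months.

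Finally, one could say that a single added word cures the mismatch and that a baseline covariate is a separate matter of efficiency. The word does settle the definition. The covariate goes further: it makes the level and change analyses give the same arm effect, and it improves precision.

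**Conclusion.** The mismatch is real, is in the current text of both documents, and is not settled by the analysis section. Its severity is minor. It concerns one secondary outcome and leaves the sample size and the primary conclusions untouched.

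Its practical weight depends on assumptions outside the documents: the ODI SD, the correlation over 12 months, the alpha for secondary outcomes, and the true effect. It matters if the 12-month effect is around 1 to 3 points or if enrolment leaves the arms unequal at baseline. At the plan's 6 points it hardly matters. Whether enrolment will in fact differ by arm cannot be known from the documents; the design only makes it possible.

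There is no matching contradiction for EQ-5D or self-efficacy, where text and table agree on a value at 12 months.

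**What to change.** In protocol 9.1 and SAP section 1, define the outcome as change in ODI from baseline to 12 months, in the prose and in the tables. In protocol 10.1 and the SAP analysis plan, state that the 12-month ODI model uses an identity link and includes baseline ODI as a covariate. The arm coefficient is then the same for either response: if Y = a + bT + cB, then Y − B = a + bT + (c − 1)B, with b unchanged.

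For consistency, treat the three-month ODI model the same way; otherwise one instrument is analysed in two ways. As a separate gain in precision, not the correction of a contradiction, include the baseline value in the 12-month EQ-5D and self-efficacy models.

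The cost is wording only. All three baselines are collected at month 0 (protocol Table 3) and are already in the imputation list.
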